6.7 BASELINE, TIME WINDOWS AND CALCULATED VISITS

The baseline visit is defined as the physical visit where the patient is enrolled in the registry program. See [Section 6.1.2](#) for definition of antithrombotic treatment status at baseline.

For other medications, medication status at day of Baseline visit is used to derive medication variables for analysis (i.e. for medication which is documented via start/stop dates: if “treatment start date \leq baseline visit \leq stop date”, patient will be flagged as being on the co-medication; for medication which is documented via tick-boxes: the same rule will be applied after imputing treatment start/ stop date with the date of visit where treatment is documented to be started/ stopped).

6.8 CALCULATION OF TIME TO EVENTS OR CENSORING

The derivations of time to event and time to censoring for the time to event analyses are specified in this section. The information from the outcome event pages will be used to collect events. Deaths reported via the vital status or serious adverse event page will also be included.

Events to be counted in the study period are all events with onset date \leq patient’s study termination date. Events occurring after the patient’s study termination date will NOT be included in the analysis (irrespective of whether they occur during the washout period or later) as treatment information will in general not be documented in the CRF for this time period. The event death is an exception. Death captured via the vital status page will still be considered after the patient’s discontinuation.

For composite outcome events, the onset date of the first occurring component event will be used.

The following rules will be used for the main analysis of outcome events:

The analysis will be based on the antithrombotic treatment choice selected at baseline (long-term treatment information, as collected in the following CRF question: “Please report any antithrombotic treatments that you prescribed for long term use at the time of the baseline visit, or any antithrombotic treatments that the patient was already on at the time of the baseline visit that the patient will remain on for long term use”) and the initial treatment regimen episode (as specified in [Section 6.1.2](#)). An event will be counted for the main analysis if it occurs during the initial treatment regimen episode of the antithrombotic therapy selected at baseline.

The time to event will be calculated as: event date - initial treatment regimen episode start date + 1.

The time to censoring will be calculated as initial treatment regimen episode stop date - initial treatment regimen episode start date + 1 (as described in [Table 6.1.2:1](#)).

Patients participating in a clinical trial with a drug or device or in another international drug study or registry on the use of oral anticoagulation in AF will be censored when they enter the trial/study. The exception is with clinical studies of idarucizumab (Praxbind) where explicit provision for collection of this data has now been included.

The following rules will be used for the intention-to-treat analysis of outcome events :

The analysis will be based on the antithrombotic treatment choice selected at baseline and the study period. An event will be counted for the intention-to-treat analysis if it occurs during the study period (see exception for inclusion of death events after patient’s discontinuation, cf. [Section 6.8](#) above).

The time to event will be calculated as: event date - study period start date (=initial treatment regimen episode start date) + 1.

The time to censoring will be calculated as study period stop date - study period start date (=initial treatment regimen episode start date) + 1.

Patients participating in a clinical trial with a drug or device or in another international drug study or registry on the use of oral anticoagulation in AF will be censored when they enter the trial/study. The exception is with clinical studies of idarucizumab (Praxbind) where explicit provision for collection of this data has now been included.

For the ITT analyses, follow-up therefore begins at initial regimen episode start date and continues until occurrence of a study outcome or end of the study period, whichever occurs first (with the exception of death). Study period refers to the time from start of initial treatment regimen (see Table 6.1.2:1) to start of the post-study phase (date of study completion/discontinuation +1 day, see [Table 6.1.1:1](#) in [Section 6.1.1](#)).

Rules to be used for the analysis of adverse events (based on enrolled patients) are specified in Section 7.9.

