5. OUTCOMES

5.1 MAIN OUTCOMES

The objectives of the study are

a) To investigate the patient characteristics influencing the choice of antithrombotic treatment for the prevention of stroke in non-valvular atrial fibrillation (AF) patients.

In order to address objective a), the same variables (demographic and lifestyle factors, disease characteristics, antithrombotic treatment characteristics and other chronic concomitant medication) will be defined and classified as for the Phase II interim study report for 1160.129 (c02207362-02) [\[3\]](#). Antithrombotic treatment groups are defined in [Section 6.1](#).

b) To collect real world data on important outcome events of antithrombotic treatments for the prevention of stroke.

The following events were considered in the 1160.129 protocol as “important outcome events”:

- Stroke (hemorrhagic and ischemic, uncertain classification)
- Transient ischemic attack (TIA)
- Systemic embolism (SEE)
- Pulmonary embolism
- Myocardial infarction (MI)
- Major bleeding events (including life-threatening bleeding events; see definition in study protocol) (MBE)
- Life-threatening bleeding events (see definition in study protocol; derived from bleeding page except for fatal bleeds which are derived as all MBEs which are linked to an SAE with “outcome= fatal” and/or “seriousness code=fatal”).
- All cause death
- Vascular death

In addition, the following two composite outcomes, also defined in the 1160.129 protocol, will be analyzed:

- Stroke, systemic embolism, myocardial infarction, life-threatening bleeding events and vascular death
- Stroke, systemic embolism, myocardial infarction and vascular death (vascular composite outcome)

The outcome event analysis will primarily be based on the data collected on the outcome CRFs (event (yes/no) and date of occurrence). The only exceptions will be made for patients who died, i.e. patients with:

- fatal AEs and without the death being documented on the outcome CRF; the death will be considered in the outcome analysis with “date of death= end date of AE”.
- “vital status=dead” and without the death being documented on the outcome CRF or on an AE form; the date of death from the vital status page will be used.

During the data cleaning process, adverse events potentially indicating an outcome event with no matching entry on the outcome CRFs will be queried.

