6.1.1 Treatment regimens / study intervals

In general, if bridging is documented in the CRF, all chronic antithrombotic treatments are stopped, therefore set "antithrombotic treatment stop date = bridging start date - 1" and "Antithrombotic treatment start date = bridging stop date + 1" prior to derivation of treatment interval. Bridging documented up until two weeks after baseline visit, will however be ignored.

Table 6.1.1: 1 Treatment regimens

Regimen label	Regimen decode	Derivation for start date
Pre-treatment	Pre-treatment	minimum of date of ICF sign off, date of baseline visit and date of any AE
Treatment	VKA VKA+ASA VKA+Clopi DE 110mg bid DE110mg bid +ASA DE150mg bid DE150mg bid +ASA ASA Clopi Clopi+ASA ...<all other mono-therapies and actual observed combination therapies> None	For each day from minimum of date of ICF sign off, date of baseline visit and date of any AE, determine treatment status of patient. Combine consecutive days with same regimen decode to treatment interval.
Washout	Washout	Drug stop date +1 day, if the previous treatment was a single treatment or if all drugs administered as combined therapy are stopped simultaneously (i.e. same stop date); duration of washout is 3 days for treatments other than VKA and 6 days for VKA.
Post-study	Post-study	date of study completion/discontinuation +1 day

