None	
 Baseline visit date is start date 	minimum of { 
 start date of chronic antithrombotic treatment)-1day, date of study completion/discontinuation }

\$Treatment interruptions (due to bridging or for any other reasons) of more than 30 days are considered permanent stop of medication. Shorter treatment interruptions will be disregarded for the analysis of outcome events (i.e. patient is considered to be on continuous treatment).

*for new oral coagulants/non-VKA oral coagulants (NOACs) in general separate treatment groups for Dabigatran, Rivaroxaban, Apixaban and Edoxaban will be presented. NOAC_X stands for one specific NOAC out of the following: Dabigatran, Rivaroxaban, Apixaban, or Edoxaban

For the sensitivity analysis of outcome events according to the intention-to-treat approach (analysis by carrying forward antithrombotic treatment at baseline), patients will not be censored after index treatment discontinuation (for additional details, see [Section 6.8](#); in particular, an exception is the event death, i.e. death captured via the vital status page will still be considered after the patient's discontinuation). This analysis is based on the same patient set as the main analysis (i.e. the "restricted" and "matched" patient sets, only including those who took at least once the treatment, see [Section 6.3](#)). Study period refers to the time from start of initial treatment regimen (see [table above](#)) to start of the post-study phase (see [Table 6.1.1:1](#) in [Section 6.1.1](#)).

Furthermore (1160.129 only), regarding baseline data and incidence rate analyses, the cohort of patients initiating (Combinations with) DE – excluding combinations with other (N)OACs (this group is part of first definition shown in [Table 6.1.2:1](#)), at baseline will be further stratified by Dabigatran mono vs combi-therapy and by dose. Additionally, the outputs by dose will be broken down by US and Non-US patients (as the 75mg dose is only approved for SPAF in US). The analyses regarding baseline data will be performed for the categories with at least 100 patients at baseline. The analyses regarding incidence rates will be performed at least for the main composite outcome for the categories with at least 500 patients at baseline. Analysis periods for analyses of outcome events are defined as follows:

Table 6.1.2: 2 Treatment regimen episode start and stop (mono/combi therapy and by dose)

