6.6 HANDLING OF MISSING DATA AND OUTLIERS

In general missing data will be handled by imputation. If cause of death is missing (neither provided on the patient vital status page nor on the outcome events page) the death will be considered as "death of unknown cause" during the data collection. If a reason of death is not

entered on the outcome CRF page but only in the free text field on the vital status page (vital status page is only to be filled for patients who discontinued the study early but allowed for vital status follow up), a medical review will be done to classify the death into vascular/non-vascular/unknown death. The classification will be documented prior to final database lock in the report planning meeting/database lock meeting minutes. For the outcome analyses regarding vascular death, as the primary approach, multiple imputation will be used to impute the unknown cause of death using the data of patients who died. The following further two alternative approaches will be considered as sensitivity analyses: (1) Unknown cause of death will be imputed as a vascular cause; (2) Unknown cause of death will be imputed as a non-vascular cause. As an additional optional sensitivity analysis for the composite outcomes, all cause death would replace vascular death ([Section 7.6](#)).

Incomplete/Missing information on outcome event occurrence / medication due to changes in visit schedule

Missed visits and visits outside visit schedule (see protocol): The CRF is set up in such a way that investigators have to enter all outcome event information and changes in medication since the last study visit; therefore complete information on outcome events is ensured even if intermittent visits are missed by using all available information from the completed study visits.

Missing outcome event date information:

The handling of missing outcome event date will be handled on a patient by patient basis. If the outcome event date for a patient is missing, all collected data for this patient will be reviewed to recover the missing outcome event date. If no information is available, the date of the outcome event will be imputed with the start of the initial treatment regimen episode+1day, if the event was documented in the first follow up visit; and with the visit date of the previous follow up visit, otherwise. The proportion of patients with partial dates will be evaluated.

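### ITT outcomes that include death count deaths after study discontinuation, but no matching end of follow-up is stated for patients known to be alive

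*SAP*

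**What the plan says.** SAP 6.8 stops counting every outcome at the patient's study termination date, with one exception: "Death captured via the vital status page will still be considered after the" patient has left the study. SAP 6.1.2 repeats this for the ITT sensitivity analysis: "in particular, an exception is the event death, i.e. death captured via the vital status page will still be considered". Where a death is known only from that page, SAP 5.1 states that "the date of death from the vital status page will be used". SAP 6.6 explains who has one: "vital status page is only to be filled for patients who discontinued the study early but allowed for vital status follow up".

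For follow-up time, the ITT rules in SAP 6.8 give a single formula: "The time to censoring will be calculated as study period stop date - study period start date", plus one day. The study period runs until the post-study phase begins, which Table 6.1.1:1 sets at "date of study completion/discontinuation +1 day". The ITT rules then say that follow-up runs to an outcome or to the end of the study period, "whichever occurs first (with the exception of death". The parenthesis closes there and names no later date.

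The as-treated main analysis has its own rule: "An event will be counted for the main analysis if it occurs during the initial treatment regimen episode". Table 6.1.2:1 ends that episode no later than study completion or discontinuation.

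SAP 7.6 plans ITT rates, cumulative risks and Kaplan-Meier curves in the restricted and matched sets. Item 2) d adds an ITT Cox model for the main composite.

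**The concern.** A patient who leaves the study and later dies contributes an event, and time up to the death. A patient who leaves and is confirmed alive on the same page is censored on the day of leaving. Time after discontinuation therefore enters the denominators and risk sets only through people who die. If leaving is unrelated to risk, ITT death rates and Kaplan-Meier risks come out too high.

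The composites have a second imbalance: after discontinuation vascular deaths still count, but strokes, infarctions and bleeds do not.

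These are sensitivity outputs, but they carry weight. ITT is one of only two sensitivity analyses of the main composite kept for 1160.136 (SAP 7.6, item 2), and Protocol 3.2.1 names an ITT analysis as the check on changing risk and adherence. A reader comparing as-treated with ITT death rates could mistake a censoring artefact for an effect of stopping treatment.

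**Working it through.** **Text check.** Three statements (SAP 6.1.2, and twice in 6.8) admit late deaths. One formula (SAP 6.8 with Table 6.1.1:1) sets ITT censoring, and it ends at study completion or discontinuation. Nothing in the available text defines a last-known-alive date as a censoring date or caps late deaths. The three-year follow-up, the registry period to June 2020 (Protocol 3.1) and database lock bound data collection, but none is stated as an analysis cut-off for these deaths.

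**Size.** The plan has no figure to reproduce. Apart from the three-year follow-up, every input is an assumption: constant hazards, T = 3 years, death μ = 0.04 per year, study discontinuation d = 0.10 per year independent of risk, and vital-status capture c = 100%, 50% or 25%. Tracing length after leaving at time t is L(t) = min(0.5, 3 − t) for 6 months, or L(t) = 3 − t for month 36.

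All-cause death, per patient, with k = μ + d = 0.14:

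- On-study time = (1 − e^(−3k))/k = (1 − e^(−0.42))/0.14 = 2.4497 years. On-study deaths = 0.04 × 2.4497 = 0.0980.
- Late deaths at full capture = ∫₀³ d·e^(−kt)·(1 − e^(−μL)) dt = 0.00452 (6 months) or 0.01509 (month 36).
- Late time of those decedents = ∫₀³ d·e^(−kt)·[(1 − e^(−μL))/μ − L·e^(−μL)] dt = 0.00110 or 0.01530 years.
- Rate under the written rule = 100 × (on-study deaths + c × late deaths) / (on-study time + c × late decedent time).
- Full capture, 6 months: 100 × 0.10251/2.45077 = 4.18. Full capture, month 36: 100 × 0.11308/2.46497 = 4.59.
- If equally traced living patients also stay at risk to month 36, the added time is 0.3773 years, and 100 × 0.11308/2.8270 = 4.00, the true rate.

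For the main composite I assumed 1.5 vascular deaths plus 2.5 non-fatal events per 100 patient-years, with only vascular deaths counted late and non-vascular death left out. Late vascular deaths are 0.0017 (6 months) or 0.0058 (month 36) per patient.

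| Outcome (true value) | 6 months' tracing, capture 100/50/25% | To month 36 (outer bound) |
|---|---|---|
| All-cause death, per 100 PY (4.00) | 4.18 / 4.09 / 4.05 | 4.59 / 4.29 / 4.15 |
| 3-year Kaplan-Meier death risk (11.31%) | 11.80 / 11.56 / 11.43% | 12.98 / 12.15 / 11.73% |
| Vascular death, per 100 PY (1.50) | 1.57 / 1.53 / 1.52 | 1.73 / 1.61 / 1.56 |
| Main composite, per 100 PY (4.00) | 4.07 / 4.03 / 4.02 | 4.23 / 4.11 / 4.06 |

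Keeping known-alive patients at risk does not repair the composite, because their later non-fatal events are not counted: to month 36 it gives 3.66 / 3.82 / 3.90 against 4.00.

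**Hazard ratio for the composite** (value at which the expected Cox score is zero; capture 100/50/25%):

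- No true difference, discontinuation 10% against 5% per year: 1.01 / 1.00 / 1.00 with 6 months' tracing; 1.03 / 1.01 / 1.01 to month 36.
- Equal discontinuation (10%) and capture, treatment acting only on non-fatal events (HR 0.70; vascular death HR 1.0): the true composite HR is (1.5 + 0.70 × 2.5)/4.0 = 0.8125. The written rule gives 0.823 / 0.818 / 0.815 to month 36.
- Equal discontinuation and capture, same effect on all components: a true 0.80 stays 0.80.

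**Informative discontinuation** (hazards change on leaving; tracing to month 36; capture 100/50/25%). Extended means known-alive patients stay at risk.

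| Scenario and outcome | Truth | Written rule | Extended | Stop at discontinuation |
|---|---|---|---|---|
| Doubled, death | 4.52 | 5.12 / 4.57 / 4.28 | 4.52 / 4.28 / 4.14 | 4.00 |
| Doubled, composite | 4.52 | 4.45 / 4.22 / 4.11 | 3.87 / 3.93 / 3.96 | 4.00 |
| Halved, composite | 3.73 | 4.11 / 4.06 / 4.03 | 3.55 / 3.76 / 3.88 | 4.00 |

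**The case against.** The best reply is that the exception is deliberate. It is stated three times, and counting known deaths after dropout is a defensible choice. The parenthesis in the ITT rule suggests that follow-up for death was meant to run longer. If sicker patients leave, the written rule can also be the closest of the three, as the doubled-hazard composite shows at every capture level. This stands as a reason not to call the rule biased upward in every case. It does not supply the missing date: a programmer following the explicit formula would censor living patients at discontinuation.

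The effect on the comparison is also small. With an assumed 2,000 patients per arm there are about 4,000 × 0.098 = 392 composite events, so SE(log HR) ≈ 2/√392 ≈ 0.10. A hazard ratio error of 1.03 (log 0.03) is about 0.3 of a standard error. The study has no confirmatory testing (Protocol 7.2). No tracing programme to month 36 is described, and some patients leave by withdrawing consent, so full capture to month 36 is an outer bound. This stands and limits the severity.

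The disposition summary in SAP 7 already reports vital-status availability by treatment. That helps interpretation but sets no censoring rule.

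**Conclusion.** The gap is real and of minor to moderate importance. For four ITT outcomes the plan counts deaths after discontinuation without an end of follow-up for patients known alive and without an analysis cap. If leaving is independent of risk, absolute ITT death rates and risks are inflated: by about 1-5% for all-cause death with 6 months' tracing (4.05-4.18 against 4.00), and by about 4-15% at the month-36 outer bound (4.15-4.59). The composites are inflated less. All of this rests on assumed discontinuation, capture and tracing.

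Four stronger readings are not supported:

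- A reader might infer that the main comparison is affected. It is not, because as-treated events must fall within the initial treatment episode. ITT non-fatal outcomes taken alone are also unaffected.
- A reader might infer that the hazard ratio is safe whenever discontinuation and capture are equal between arms. It also needs the same treatment effect on all components, although the shift otherwise is only about 1%.
- A reader might infer that the rule always overstates risk. Under informative discontinuation it may lie above or below the truth.
- A reader might take item 2) d to be the only ITT Cox model. Some sections are not in the public documents, so this cannot be confirmed.

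**What to change.** In SAP 6.1.2 and 6.8, replace the parenthesis about death with one stated end of follow-up and one cap, for example the planned 36 months, applied equally to dead and living patients.

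- **ITT all-cause death:** count deaths up to the cap, and censor patients known alive at their last vital-status date under the same cap. If no such date is recorded, end at study discontinuation for everyone and report later deaths separately.
- **ITT vascular death and both composites:** end follow-up at study discontinuation, because non-fatal events are not counted later. A version that adds later vascular deaths is optional and should be labelled as such.
- **Interpretation:** read the results against the vital-status availability summary already planned in SAP 7, and state that no version is unbiased in general under informative discontinuation.

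The all-cause death rule recovers the true rate under independent discontinuation only if the dead and the living are traced equally well. With 50% of the dead but 25% of the living traced to month 36, it gives 4.14 against 4.29 under the written rule and a true 4.00.

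The cost is SAP wording and one derived censoring variable, with no new data collection. The composite version that ends at discontinuation leaves out late vascular deaths. Under the assumed inputs, per 2,000 patients, these number about 3/2/1 with 6 months' tracing or 12/6/3 to month 36, at 100/50/25% capture (for example 2,000 × 0.0058 ≈ 12).

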3.3.4 Removal of patients from therapy or assessments

3.3.4.1 Removal of individual patients

A patient can be withdrawn from the registry for the following reasons:

- A patient or legally accepted representative withdraws consent
- The patient was erroneously included in the Registry Program
- Participation in another international drug study or registry on the use of oral anticoagulation in AF
- Participation in a clinical trial with a drug or device
- Any other reason as agreed to by the Investigator and the BI Clinical Monitor

The Clinical Monitor at BI or BI's designees must be immediately notified if a patient is discontinued prematurely for any of the reasons cited above. The Investigator will indicate on the End of Study form page the reason/s for discontinuation. If a patient discontinues the study prematurely, another follow-up assessment should be performed if possible (unless the reason for discontinuation is erroneous enrollment of the patient into the study at baseline), and data should be entered on the eCRFs of the next planned visit.

Patients should NOT be discontinued from the registry study due to an SAE or a non-serious AE unless the patient withdraws their consent to participate in the study. Ongoing information on adverse events is important data that should be collected on all patients who are being followed up, for the full duration of the follow-up period.

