6.2.2 Assessments in Phase III of GLORIA-AF

In Phase III a baseline assessment is performed for all patients, identical to the baseline assessments for Phase II as described in Section [6.2.1](#).

Follow-up assessments will be done for ALL patients (i.e. irrespective of antithrombotic treatment status).

Assessments at Follow-up Visits:

Follow-up visits: 6-month, 12-months (1 year), 24-months (2 years) and 36-months (3 years) after Baseline visit.

- Date of follow-up visit
- Type of follow-up visit
- Concomitant diseases (current, any changes)
- Serum creatinine to be recorded (if available)
- Antithrombotic treatment (current, any change (start and stop dates) including compliance, reason for change; including interruptions of antithrombotic treatment due to therapeutic/diagnostic interventions)
- Selected concomitant treatment (current, any change)
- Patients receiving VKAs: the last three INR values and dates performed, from files and if necessary by contacting INR clinics, hospitals, etc.
- Information about VKA therapy such as location of INR testing (physician's office, freestanding lab, home testing), including discontinuations and re-starts, dates, reasons for changes, etc.
- Outcome events as listed in [Section 5.1](#)
- Information is recorded on any therapeutic/diagnostic interventions that occur as part of regular follow-up
- All serious adverse events judged as related or unrelated to any drug (see [section 5.2.2.2](#))
- Non-serious adverse events judged as related to any antithrombotic therapy including dabigatran, or to any BI drug (see [section 5.2.2.2](#))
- Vital status (only at last follow-up visit)

If a patient prematurely discontinues from the registry, a follow-up assessment should be performed at time of study discontinuation if possible, and the end of study eCRF completed.

Proprietary confidential information.

© 2014 Boehringer Ingelheim International GmbH or one or more of its affiliated companies. All rights reserved.

This document may not - in full or in part - be passed on, reproduced, published or otherwise used without prior written permission.

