6.2.3 End of study and follow-up period

For early Discontinuation:

- Date of Registry discontinuation
- Reason for Registry discontinuation
- Vital status

Proprietary confidential information.

© 2014 Boehringer Ingelheim International GmbH or one or more of its affiliated companies. All rights reserved.

This document may not - in full or in part - be passed on, reproduced, published or otherwise used without prior written permission.

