6.1.2 Specification of treatments for analyses

Reference time periods for the analysis of outcome events, exposure time, AEs are specified in the study protocol:

A patient is considered to have permanently stopped initial antithrombotic treatment according to the definition of antithrombotic treatment start and stop date provided in [Table 6.1.2:1](#).

For the main analysis (as treated analysis) of outcome events, patients will be grouped according to the therapy prescribed for long term treatment at baseline visit, excluding patients who never took the prescribed medication. This will be derived based on the CRF question on planned long-term AF treatment documented at baseline. The number and percentage of patients who never took the prescribed medication (defined as not taken one single dose of prescribed medication) will explicitly be shown in the disposition table (see [Table 6.4:1](#)); they will be excluded from all main outcome analyses if they did not take the treatment group defining medication (e.g. a patient prescribed to VKA+Clopidogrel which took only VKA will be grouped as a VKA patient; a patient prescribed to VKA+Clopidogrel and took only Clopidogrel will be excluded from all main outcome analyses). For potential outcome analyses patients will be included under the treatment (mono/combi) and dose they

were prescribed and actually took. Start and end of initial treatment regimen episode which will be used as analysis period for the main analysis of outcome events are defined as follows:

Table 6.1.2: 1 Treatment regimen episode start and stop

Treatment group	initial treatment regimen episode start	initial treatment regimen episode stop
(Combinations with) NOAC_X* - excluding combinations with other (N)OACS:	
The NOAC treatment start date starts active medication;
 
 if NOAC treatment start date < min(date of ICF sign off, date of baseline visit) then use min(date of ICF sign off, date of baseline visit) instead if NOAC start date is missing then use date of ICF sign-off. 	minimum{ 
 permanent stop\$ date of NOAC+3days, start date of other chronic anticoagulant treatment (i.e. VKA, new oral anticoagulants other than original NOAC) -1day date of study completion/discontinuation }

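### Follow-up runs to the study completion/discontinuation date rather than the last outcome assessment, so patients lost without a discontinuation assessment may add event-free, on-drug time that was not systematically observed

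*SAP*

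**What the plan says.** SAP 6.8 sets the main-analysis rule: "The time to censoring will be calculated as initial treatment regimen episode stop date - initial treatment regimen episode start date + 1". In SAP Table 6.1.2:1 the stop date for a treated patient is in general the earliest of permanent drug stop plus washout, the day before another anticoagulant starts, and the "date of study completion/discontinuation". Table 6.1.2:2 uses the same study-end term. The intention-to-treat period in 6.8 also ends at completion or discontinuation. None of these rules contains a last-visit or last-contact term.

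On ascertainment, SAP 6.6 says that "investigators have to enter all outcome event information and changes in medication since the last study visit". Protocol 6.2.2 gives the Phase III schedule: "Follow-up visits: 6-month, 12-months (1 year), 24-months (2 years) and 36-months (3 years) after Baseline visit".

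On early discontinuation, Protocol 6.2.3 collects "Date of Registry discontinuation", the reason and vital status. Protocol 3.3.4.1 says "another follow-up assessment should be performed if possible". Neither document says which date is entered for a patient who stops attending.

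SAP 6.8 also states: "Events occurring after the patient’s study termination date will NOT be included in the analysis". Its reason is that treatment is generally not documented for that period. Death is excepted: "Death captured via the vital status page will still be considered after" discontinuation.

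**The concern.** SAP 6.6 argues that outcome information stays complete when intermittent visits are missed, because the next completed visit looks back over the gap. A patient lost for good has no next visit. If no discontinuation assessment takes place, the time from the last completed visit to the recorded discontinuation date enters the denominator as event-free. It also counts as time on index drug, because a stop or switch in that interval has no visit at which to be recorded.

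The SAP's own reason for excluding events after study termination, that treatment is not documented, applies equally to this interval.

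Incidence rates and Kaplan-Meier risks, which are main outputs in both studies, would then be too low. The dabigatran-VKA hazard ratio would be distorted if loss differs between the arms. Non-fatal events are the more exposed, since deaths can still arrive through the vital status page.

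**Working it through.** **1. Reproduce the plan's figure.** Protocol 7.6 assumes 25% per year for treatment discontinuation and loss combined, 2,000 patients per cohort and 3 years.

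- Hazard = −ln(0.75) = 0.2877 per year.
- Patient-years = 2,000 × (1 − exp(−0.2877 × 3)) / 0.2877 = 4,019, as stated.
- The Phase II figure also reproduces: 2,500 patients over 2 years give 3,802.

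The concern does not dispute these figures.

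**2. Unobserved time per patient.** Visits are at 0, 0.5, 1, 2 and 3 years. Let λ be the loss hazard and Λ the total hazard (loss plus drug stop). Sums run over visit intervals (a, b].

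- Time to loss, drug stop or 3 years: B = (1 − e^(−3Λ)) / Λ
- Unobserved time if the true moment of loss is entered: G = Σ ∫ λ e^(−Λt) (t − a) dt
- Unobserved time if the next due visit is entered: G2 = Σ ∫ λ e^(−Λt) (b − a) dt
- Observed share of counted time: (B − G)/B, or (B − G)/(B − G + G2)

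The loss rates are assumptions, because the protocol does not split its 25%. Every event in the gap is treated as missed, so these are upper bounds for each dating rule. Example with 5% annual loss and no drug stop: B = 2.7806, G = 0.0584, G2 = 0.1176 years, and 0.1426 of patients are lost.

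- True-loss dating: 2.7222/2.7806 = 0.979
- Next-visit dating: 2.7222/2.8398 = 0.959
- Mean gap per lost patient: 12 × 0.0584/0.1426 = 4.9 months, or 12 × 0.1176/0.1426 = 9.9 months

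| Assumed annual loss | Observed share, true-loss dating | Observed share, next-visit dating |
|---|---|---|
| 2% | 0.992 | 0.983 |
| 5% | 0.979 | 0.959 |
| 10% | 0.958 | 0.918 |

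Adding a 20% annual drug-stop rate changes little: 0.992, 0.981, 0.961 and 0.98, 0.96, 0.92. If last contact is entered, or an assessment takes place on the recorded date, the share is 1.

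**3. Against the plan's 25% attrition (2,000 patients, 3 years).** The share of attrition that is loss is assumed. A true rate of 3.0 per 100 patient-years is the top of the protocol's expected range for stroke/SEE and major bleeding.

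| Loss as share of attrition | Observed PY | Unobserved PY, true-loss | Unobserved PY, next-visit | Rate of 3.0 appears as |
|---|---|---|---|---|
| 10% | 3,976 | 43 | 91 | 2.97 / 2.93 |
| 25% | 3,911 | 109 | 227 | 2.92 / 2.84 |
| 50% | 3,802 | 217 | 453 | 2.84 / 2.68 |
| 100% (extreme) | 3,585 | 434 | 906 | 2.68 / 2.40 |

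**4. Comparison between arms.** Equal loss leaves a true ratio of 1.00 unchanged. At an assumed 8% versus 3% annual loss with no drug stop, it appears as 0.9663/0.9874 = 0.98 (true-loss) or 0.934/0.9751 = 0.96 (next-visit), in favour of the arm that loses more.

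**5. What sensitivity analysis (e) catches.** SAP 7.6 item 2(e) censors at the last physical visit if more than one consecutive physical visit is missed, or if the last visit was by telephone. A patient seen in person at month 24, then lost and closed by month 36, misses at most one visit and is not caught. A patient seen at month 12 and closed at month 24 is caught only if visits due after discontinuation count as missed, which the SAP does not say. For 1160.136 only (d) and (f) are run. (d) is the intention-to-treat analysis and ends on the same date.

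**The case against.** The strongest reply is that the bias is conditional. The documents reviewed do not include eCRF completion instructions or the data management plan, which might define the discontinuation date as last contact. Protocol 3.3.4.1 and 6.2.2 ask for an assessment at discontinuation, and nothing shows how often it fails. This stands.

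Ascertainment between visits is also weaker rather than absent. Protocol 5.2.2 collects all serious and outcome events from consent until 6 days after the last follow-up visit, with rapid reporting of causally related ones. SAP 5.1 queries adverse events that suggest an unrecorded outcome, and brings in deaths from adverse event and vital status forms. This stands too, and makes the working an upper bound for each dating rule.

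The comparative effect is small beside sampling error. With 4,019 patient-years per arm and 1 to 3 events per 100, there are about 40 to 121 events per arm. A 95% interval around a ratio of 1, exp(±1.96 √(2/events)), is about 0.65 to 1.55 or 0.78 to 1.29. The analyses are descriptive, and losses are counted and characterised (SAP 6.6, 7.4). That limits the weight of the point. It does not remove a systematic error in the rates.

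A reader might infer more: that every lost patient adds time nobody observed, that the hazard ratio is biased, or that persistence is overstated. The documents do not support these. The first depends on unstated dating practice, the second on unequal loss that is nowhere documented, and the third on SAP 7.7, which is not in the text available.

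**Conclusion.** The point holds as a conditional weakness in a stated rule. Both analysis periods end at the discontinuation date, the completeness argument in SAP 6.6 does not reach patients lost after their last visit, and (e) protects only some of them, in 1160.129 alone.

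The effect ranges from nil to rates understated by about 1%, 2% and 4% (true-loss dating) or 2%, 4% and 8% (next-visit dating) at 2%, 5% and 10% annual loss. Careless dating is not needed: an accurate date of loss without an assessment still leaves about 5 unobserved months per lost patient. The hazard ratio is affected only under unequal loss, by about 2% to 4% in the example.

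These sizes rest on assumed loss rates, constant hazards, visits on schedule and no capture of events in the gap. The change is worth making because it is cheap and the present rule can only err towards favourable rates.

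**What to change.** - **Main rule.** In Tables 6.1.2:1 and 6.1.2:2 and in SAP 6.8, for patients alive at study end without a completed final or discontinuation assessment, replace the study completion/discontinuation date with the date of the last visit or contact, physical or telephone, at which outcomes and treatment were recorded. Apply this to the as-treated and intention-to-treat periods, in both 1160.129 and 1160.136.
- **Deaths.** Keep deaths, and fatal events documented on the outcome, SAE or vital status pages, in the main analysis under the existing rules of SAP 5.1 and 6.8. Follow-up for those patients runs to death or to the existing episode stop. Without this sentence the new cap could remove deaths between visits and push rates the wrong way.
- **Sensitivity analysis.** Keep the current discontinuation-date censoring as a sensitivity analysis in both studies, including non-fatal events documented after the last contact.
- **Reporting.** Tabulate the gap between last contact and discontinuation date by treatment group. If it is near zero, the issue is closed.

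The cost is SAP wording and one derived date from visit dates already collected. Patient-years fall slightly and rates become slightly less favourable.
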